14.2 Adverse Event Details

AEs may be either spontaneously reported or elicited during questioning and examination of a subject. All AEs must be recorded on the AE eCRF. If known, the investigator should report the diagnosis of the underlying illness or disorder, rather than its individual symptoms. Subjects experiencing AEs that cause interruption or discontinuation of test article or those experiencing AEs that are present at the end of their participation in the study should receive follow-up as appropriate. AEs should be followed to resolution or

stabilization (if possible) and, if they become serious, reported as serious adverse events (SAEs, see [Section 14.3](#)). If possible, the outcome of any AEs that caused permanent discontinuation or that were present at the end of the study, especially those considered by the investigator to be related to the test article, should be reported.

Information on the medical condition of subjects should begin following the subject's written informed consent to participate in the study and a medical history should be taken at screening. During any wash out and baseline periods, any changes in the health of subjects should be recorded as changes in medical history unless an event occurred as a result of a study-related procedure and is unanticipated; in such cases, the event should be recorded as an AE and reported to the Institutional Review Board (IRB) as an "unanticipated problem" in accordance with local procedures. Other changes in subject health information becomes AE data when the subject begins dosing with the test article; therefore AE data should be collected from the date of the first dose of test article until the date of the final study visit. These data are considered treatment-emergent AEs.

The investigator will instruct the subject to report any AEs that may occur during the study. At each visit, the investigator should ask the subject, in non-directive fashion, about any change in the subject's overall health status since the previous visit.

The severity of each AE, as judged by the investigator, will be recorded on the appropriate AE eCRF and will be graded according to the following scale:

Mild - The AE is usually transient and may require only minimal treatment or therapeutic intervention. The event does not generally interfere with usual activities of daily living.

Moderate - The AE is usually alleviated with additional specific therapeutic intervention. The event interferes with usual activities of daily living, causing discomfort, but poses no significant or permanent risk of harm to the research participant.

Severe - The AE interrupts usual activities of daily living or significantly affects clinical status, or may require intensive therapeutic intervention.

The investigator must determine the relationship of the AE to the test article according to the following categories:

Definitely Related - An event that follows a reasonable temporal sequence from administration of the test article; that follows a known or expected response pattern to the test article; and that is confirmed by improvement on stopping or reducing the dosage, and reappearance of the event on repeated exposure (re-challenge).

Probably Related - An event that follows a reasonable temporal sequence from administration of the test article; that follows a known or expected response pattern

to the test article; and that is confirmed by improvement on stopping or reducing the dosage of the test article; and that is unlikely to have been caused by concurrent/underlying illness or other drugs, procedures, or other causes.

Possibly Related - An event that follows a reasonable temporal sequence from administration of the test article; that follows a known or expected response pattern to the test article; but may have been caused by concurrent/underlying illness, other drug, procedure, or other causes.

Unlikely Related - An event that does not follow a reasonable temporal sequence from administration of the test article; that does not follow a known or expected response pattern to the test article, or most likely was caused by concurrent/underlying illness, other drug, procedure, or other causes, because of their known effects.

Not Related - An event almost certainly caused by concurrent/underlying illness, other drug, procedure, or other causes.

The investigator should categorize the outcome of the AE according to the following categories:

Fatal - Termination of life as a result of an AE.

Not Recovered/Not Resolved - AE has not improved or the subject has not recuperated.

Recovered/Resolved - AE has improved or the subject has recuperated.

Recovered/Resolved with Sequelae - subject recuperated but retained the pathological conditions resulting from the prior disease or injury.

Recovering/Resolving - AE is improving or the subject is recuperating.

Unknown - Not known, not observed, not recorded or subject refused.

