13.2 Subject Discontinuation

A subject may be withdrawn from the study prior to completion for any of the following reasons:

- AEs
- Death
- Lack of efficacy (defined as the lack of expected or desired effect related to a therapy)
- Lost to follow-up
- Non-compliance with study drug
- Physician decision
- Pregnancy
- Progressive disease (defined as a disease process that is increasing in extent or severity)
- Protocol deviation
- Study terminated by Sponsor

- Withdrawal by subject; NOTE: if the subject decides to withdraw from the study due to an AE then it should be classified as withdrawal due to an AE
- Other (e.g., any reason that may affect the outcome of the study or safety of subjects)

If a subject withdraws from the study prematurely for any reason, the site should make every effort to have the subject return to the clinic to perform all of the required visit activities for Visit 6 if the subject is withdrawing during the treatment phase of the study or Visit 9 if the subject is in the post-treatment follow-up phase of the study and to collect and reconcile all test articles (if applicable). If the subject will not return to the clinic, the site should make every attempt to contact the subject; otherwise the subject will be considered lost to follow-up.

When a subject is withdrawn from the study for a test article related AE (as defined in [Section 14.2](#)), when possible, the subject should be followed until resolution or stabilization of the AE. If the subject is discontinued from the study due to pregnancy, the pregnancy and its outcome should be followed.

Subjects who are prematurely withdrawn or discontinued from the study will be replaced until approximately 20 subjects have completed the study.

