14. ADVERSE EVENT REPORTING

14.1 Adverse Event Definitions

An **adverse event** is any untoward medical occurrence associated with the use of a drug in humans, whether or not considered drug related.

An AE (also referred to as an adverse experience) can be any unfavorable and unintended sign (e.g., an abnormal laboratory finding), symptom, or disease temporally associated with the use of a drug, without any judgment about causality. An AE can arise from any use of

the drug (e.g., off-label use, use in combination with any drug) and from any route of administration, formulation, or dose, including an overdose.

A suspected adverse reaction is any AE for which there is a reasonable possibility that the drug caused the event. "Reasonable possibility" means there is evidence to suggest a causal relationship between the drug and the AE.

An **adverse reaction** is any AE caused by a drug. Adverse reactions are a subset of all suspected adverse reactions for which there is reason to conclude that the drug caused the event. A suspected adverse reaction implies a lesser degree of certainty about causality than adverse reaction, which means any AE caused by a drug. For the purposes of prescription drug labeling, the term adverse reaction means an undesirable effect, reasonably associated with the use of a drug that may occur as part of its pharmacological action or may be unpredictable in its occurrence.

An AE or suspected adverse reaction is considered "unexpected" if it is not listed in the Investigator Brochure (IB) or is not listed at the specificity or severity that has been observed; or, if an IB is not required or available, the event is considered "unexpected" if it is not consistent with the risk information described in the general investigational plan or elsewhere in the current application. For example, under this definition, hepatic necrosis would be unexpected (by virtue of greater severity) if the IB referred only to elevated hepatic enzymes or hepatitis. Similarly, cerebral thromboembolism and cerebral vasculitis would be unexpected (by virtue of greater specificity) if the IB listed only cerebral vascular accidents. "Unexpected," as used in this definition, also refers to AEs or suspected adverse reactions that are mentioned in the IB as occurring with a class of drugs or as anticipated from the pharmacological properties of the drug, but are not specifically mentioned as occurring with the particular drug under investigation.

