14.3 Serious Adverse Event

An event that is serious must be recorded on the AE eCRF and on the ^P SAE Report Form, and requires expeditious handling to comply with regulatory requirements.

An AE or suspected adverse reaction is considered “serious” if, in the opinion of either the investigator or Sponsor, it results in any of the following outcomes:

- Death; the event must be the cause of death for the SAE to meet this serious criterion.

- Life-threatening event; an event in which the subject was at risk of death at the time of the event and not an event that hypothetically might have caused death if it had been more severe.
- Requires inpatient hospitalization or prolongation of existing hospitalization (for ≥ 24 hours).
- Persistent or significant incapacity or substantial disruption of the ability to conduct normal life functions.
- Congenital anomaly/birth defect.
- Important medical events; a medical event(s) that may not result in death, be life-threatening, or require hospitalization but, based upon appropriate medical judgment, may jeopardize the subject and may require medical or surgical intervention to prevent one of the outcomes listed in the definition above. Examples of such medical events include allergic bronchospasm requiring intensive treatment in an emergency room or at home, blood dyscrasias or convulsions that do not result in inpatient hospitalization, or the development of drug dependency or drug abuse.

Events NOT considered to be SAEs are:

- Hospitalizations for the treatment, which was elective or pre-planned, of a pre-existing condition that did not worsen; and
- Treatment on an emergency, outpatient basis, for an event not fulfilling any of the definitions of “serious” given above and not resulting in hospital admission.

AEs classified as “serious” by either the investigator or the Sponsor require expeditious handling and reporting to ^P to comply with regulatory requirements. **All SAEs, whether related or unrelated to test article, must be immediately reported by telephone to the Medical Monitor and, in the event that he/she is unavailable, to the Project Manager listed on the first page of the protocol.** Written notification of all SAEs should be sent to the Project Manager by email or confirmed facsimile transmission. These include those SAEs listed in the protocol or IB and must include an assessment of whether there is a reasonable possibility that the test article caused the event.

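### Section 14.2 makes a known or expected response pattern a condition of every related category, so a new type of reaction cannot be recorded as related, contrary to Sections 14.1 and 14.3

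*Combined protocol and SAP*

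**What the plan says.** Section 14.2 is directive: "The investigator must determine the relationship of the AE to the test article according to the following categories". The five categories are Definitely, Probably, Possibly, Unlikely and Not Related.

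- Definitely Related asks for plausible timing and an event "that follows a known or expected response pattern to the test article; and that is confirmed by improvement on stopping or reducing the dosage", plus reappearance on re-exposure.
- Probably Related opens in the same way: "Probably Related - An event that follows a reasonable temporal sequence from administration of the test article; that follows a known or expected response pattern". It then adds improvement on stopping or reducing the dosage, and that other causes are unlikely.
- Possibly Related asks for plausible timing and an event "that follows a known or expected response pattern to the test article; but may have been caused by concurrent/underlying illness, other drug", among other alternatives.
- Unlikely Related names implausible timing, then an event "that does not follow a known or expected response pattern to the test article, or most likely was caused by concurrent/underlying illness", among other alternatives.
- Not Related requires an almost certain other cause.

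Section 14.1 sets the standard differently: "A suspected adverse reaction is any AE for which there is a reasonable possibility that the drug caused the event". It deals with unexpectedness in its own paragraph, mainly by comparison with the Investigator Brochure, and applies that term to suspected reactions as well as to adverse events. Section 14.3 says that SAE notifications "must include an assessment of whether there is a reasonable possibility that the test article caused the event", and singles out suspected reactions that are both serious and unexpected for faster reporting.

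The category is used in three places. Section 17.3.2 includes causality in the first safety endpoint. Section 17.4.2 summarizes adverse events by relationship and treatment group. Section 13.2 refers to 14.2 for the meaning of a related event when it says that, after withdrawal for such an event, "when possible, the subject should be followed until resolution or stabilization of the AE".

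**The concern.** Whether a drug caused an event and whether the event was already known are two different questions. Section 14.1 keeps them apart; the scale in 14.2 joins them. An event can then be a suspected adverse reaction under 14.1 and still be barred from every related category under 14.2.

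This matters more than usual here for two reasons. Section 10.2.3 sends any local skin reaction outside the three named types (burning/stinging, edema, folliculitis) to the adverse event form, so unlisted local reactions arrive at the scale least able to call them related. And under Section 4 every subject receives both test articles, so there is no vehicle-only group against which to compare systemic events, and the investigator's attribution carries much of the weight for them.

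For an SAE, the site can answer yes to the reasonable-possibility question in 14.3 and still find no related category on the eCRF. For a non-serious event the visible text provides no second question at all. What is at stake is whether the relationship tables report what investigators actually believe about new reactions.

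**Working it through.** No figure is involved, so the check is a logical one. Take a single test event and pass it through the five definitions in 14.2.

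**Test event.** Timing plausible: yes. Improves on stopping: yes. Other cause likely or almost certain: no. Known or expected pattern: no.

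| Category | Result | Deciding condition |
|---|---|---|
| Definitely Related | fails | pattern required |
| Probably Related | fails | pattern required |
| Possibly Related | fails | pattern required |
| Unlikely Related | depends on reading | see below |
| Not Related | fails | no almost certain other cause |

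**Unlikely Related.** The definition has the form A; B, or C, where A is implausible timing, B is absence of a known pattern, and C is that another cause is most likely.

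- Reading 1, any one suffices (A or B or C): B is met, so the event is rated Unlikely.
- Reading 2, the semicolon means and ((A and B) or C): A is not met and C is not met, so Unlikely fails and no category is left.

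Reading 2 has some textual support, because in the three related categories the semicolons do join conditions that must all hold. The document does not settle the matter. Under both readings the three related categories are closed.

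**Control.** Change one input only: let the pattern be known. The event now meets every condition of Probably Related (timing, pattern, improvement on stopping, other causes unlikely). Expectedness alone therefore moves the same clinical evidence from Probably Related to Unlikely or to no category.

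**Against 14.1 and 14.3.** Under 14.1 the test event qualifies as a suspected adverse reaction if there is evidence to suggest causation; timing and improvement on stopping are evidence of that kind, and no pattern condition applies. If it is not in the Investigator Brochure it is also unexpected, which 14.1 allows. If it is serious, 14.3 asks for the reasonable-possibility assessment, to which the answer could be yes. The same event would then carry yes in the SAE report and no related category on the eCRF. The documents do not map one onto the other.

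**The case against.** The strongest reply is that the scale does less work than it seems to. Section 14.2 records all adverse events, and 17.4.2 lists them and tabulates them by system organ class, preferred term and severity as well as by relationship. The named local skin reactions are scored for each plaque, at every visit except Screening, with no causality judgement. All SAEs are reported whether related or not, with their own causality assessment. The safety summaries are descriptive, and no test, threshold or stopping rule depends on relatedness. All of this stands: a new reaction would remain visible, and only its label is affected.

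It can also be said that 14.2 does not define a known or expected pattern or tie it to the Investigator Brochure, so an investigator might accept an unlisted application-site reaction as expected for a topical solution under occlusion. That stands in part. It means the number of events affected cannot be judged, the more so because the background section is redacted. It does not help an event that nobody would call expected, and leaving the phrase to individual interpretation invites different ratings at the approximately three sites.

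Four stronger readings are tempting, and the documents do not support them.

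- A reader might infer that new reactions are always pushed to Unlikely. That holds on only one of the two readings of the punctuation; on the other, the fault is a gap in the scale.
- A reader might infer from 13.2 that a reaction not rated related loses follow-up. Section 14.2 itself provides for following adverse events to resolution or stabilization where possible, with no condition on relatedness, and for follow-up of those that lead to discontinuation of the test article. The cross-reference in 13.2 is a wording inconsistency only.
- A reader might put a figure on it: with about 20 subjects, one or two relabelled subjects would move the related-event rate by 1/20 = 5 or 2/20 = 10 percentage points. Those events are assumed, and the subject-level rate moves only if the subject has no other related event.
- A reader might object that Definitely Related needs re-exposure, which no visit schedules. That is a criterion of evidence for the top category and could be met incidentally after an interruption; it is not part of this point.

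**Conclusion.** The point holds in a limited form. As written, 14.2 closes all three related categories to an adverse event with plausible timing, no likely other cause and no known or expected pattern, whichever way Unlikely Related is read. That conflicts with 14.1, where reasonable possibility and unexpectedness are separate attributes, and with 14.3, which relies on the same distinction.

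The consequence is a wrong or missing relationship label in safety endpoint 1 and in the descriptive tables by relationship, chiefly for non-serious events of a new type. Detection and SAE reporting are intact, and follow-up is provided for elsewhere. No numerical size is available, since the documents give no adverse event rate and no count of reactions outside the known pattern.

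The conclusion assumes that investigators apply the definitions literally, as the mandatory wording asks, and that no redacted text redefines the scale. A redacted list of known reactions would not remove the problem for a reaction missing from the list. Correcting it is worthwhile because a named safety endpoint is touched and the remedy is nearly free.

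**What to change.** Reword 14.2 and the eCRF completion guidance so that causality is rated separately from expectedness:

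1. Define Possibly Related as plausible timing together with a reasonable possibility of causation, whether or not the pattern is already known.
2. For Probably and Definitely Related, treat a known pattern as supporting evidence and not as a requirement.
3. Remove absence of a known pattern as a stand-alone criterion for Unlikely Related, and punctuate what remains so that it has one reading.
4. State that Definitely, Probably and Possibly Related together correspond to the reasonable possibility of 14.1 and 14.3, so that the eCRF and the SAE report agree and the reference in 13.2 has one meaning.

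The cost is a wording change in the protocol and in the site guidance, with no added visits or assessments. The downside is that a few more events may be counted as related.

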14.3 Serious Adverse Event

An event that is serious must be recorded on the AE eCRF and on the ^P SAE Report Form, and requires expeditious handling to comply with regulatory requirements.

An AE or suspected adverse reaction is considered “serious” if, in the opinion of either the investigator or Sponsor, it results in any of the following outcomes:

- Death; the event must be the cause of death for the SAE to meet this serious criterion.

- Life-threatening event; an event in which the subject was at risk of death at the time of the event and not an event that hypothetically might have caused death if it had been more severe.
- Requires inpatient hospitalization or prolongation of existing hospitalization (for ≥ 24 hours).
- Persistent or significant incapacity or substantial disruption of the ability to conduct normal life functions.
- Congenital anomaly/birth defect.
- Important medical events; a medical event(s) that may not result in death, be life-threatening, or require hospitalization but, based upon appropriate medical judgment, may jeopardize the subject and may require medical or surgical intervention to prevent one of the outcomes listed in the definition above. Examples of such medical events include allergic bronchospasm requiring intensive treatment in an emergency room or at home, blood dyscrasias or convulsions that do not result in inpatient hospitalization, or the development of drug dependency or drug abuse.

Events NOT considered to be SAEs are:

- Hospitalizations for the treatment, which was elective or pre-planned, of a pre-existing condition that did not worsen; and
- Treatment on an emergency, outpatient basis, for an event not fulfilling any of the definitions of “serious” given above and not resulting in hospital admission.

AEs classified as “serious” by either the investigator or the Sponsor require expeditious handling and reporting to ^P to comply with regulatory requirements. **All SAEs, whether related or unrelated to test article, must be immediately reported by telephone to the Medical Monitor and, in the event that he/she is unavailable, to the Project Manager listed on the first page of the protocol.** Written notification of all SAEs should be sent to the Project Manager by email or confirmed facsimile transmission. These include those SAEs listed in the protocol or IB and must include an assessment of whether there is a reasonable possibility that the test article caused the event.

Study endpoints that are SAEs (e.g., all-cause mortality) must be reported in accordance with the protocol unless there is evidence suggesting a causal relationship between the test article and the event (e.g., death from anaphylaxis). In this case, the investigator must immediately report the event to the Sponsor. In addition, such information should also be provided to the site’s respective IRB per their governing guidelines for SAE reporting.

Any suspected adverse reactions that are serious and unexpected represent especially important safety information that must be reported more rapidly to Health Authorities; therefore, it is important that the investigator submit any information requested by the Sponsor or designee as soon as it becomes available.

If only limited information is initially available, follow-up reports are required. Should the investigator become aware of an SAE (regardless of its relationship to test article) that

occurs within 30 days after stopping the test article, the SAE must be reported in accordance with procedures specified in this protocol. In the event of death, if an autopsy is performed, a copy of the report should be sent to PP if available.

As required, the Sponsor will notify participating investigators of all suspected adverse reactions that are serious and unexpected. This notification will be in the form of an IND safety report of potential serious risks as soon as possible but no later than 15 calendar days after the Sponsor determines that the information is “reportable” according to the criteria listed in 21 CFR Section 312.32. These are:

- i) Serious and unexpected suspected adverse reactions;
- ii) Findings from other studies including epidemiological studies, pooled analyses, or other clinical studies that suggest a significant risk in humans exposed to the test articles;
- iii) Findings from animal or in vitro tests that suggest a significant risk to humans exposed to the test articles, or reports of significant organ toxicity at or near the expected human exposure; and
- iv) Clinically important increases in the rate of occurrence of serious suspected adverse reactions.

Upon receiving such notices, the investigator must review and retain the notice with the IB and promptly submit a copy of this information to the responsible IRB according to local regulations. The investigator and IRB will determine if the informed consent requires revision. The investigator should also comply with the IRB procedures for reporting any other safety information. Where required, submission of safety updates by the investigator to Health Authorities should be handled according to local regulations.

The Sponsor or designee may be required to report certain SAEs to regulatory authorities (e.g., United States FDA) within seven calendar days of being notified about the event; therefore, it is important that investigators submit any information requested by the Sponsor or designee as soon as it becomes available.

